8.2. Adjustments for Covariates and Factors to be Included in Analyses

The following covariates and factors, and/or endpoint Baseline measure are used in the analyses. For details of their inclusion in the models, refer to the specific analysis section.

- Naïve to biologic or JAK inhibitor therapy at study entry (Yes or No)
- Baseline corticosteroid use (Yes or No)
- Baseline disease activity (MMS: 4 to 6 or 7 to 9)

If a subject was assigned the wrong stratum at randomization, their stratum based on the randomization system will be used for the statistical analyses. Analyses may be repeated using actual stratum if mis-randomization occurs in more than 10% of randomized subjects.

8.3. Missing Data

Missing adverse event (AE) relationship to study treatment and AE seriousness will be imputed as described in Section 18.1.1.2 and Section 18.1.3, respectively. Partial or missing AE start dates, concomitant medication (CM) start dates, and hospitalization dates will also be imputed as described in Appendix 2. No other missing safety data will be imputed.

[figure not shown]
Missing efficacy data will be handled as described in Section 16.1.2, Section 16.2.2, and Section 16.3.2. In the primary analysis of the primary endpoint and main analyses of all binary responder-type endpoints, all subjects with missing data, regardless of reason for missingness, will be considered as nonresponders. In the main analysis of continuous or score endpoints, such as biomarker measures, urgency Numeric Rating Scale (NRS), abdominal pain NRS, and HRQoL measures, subjects with missing data will be handled using observed cases only, multiple imputation, or a mixed-effect model with repeated measures.

8.4. Multiple Comparisons and Multiplicity

There are multiple null hypotheses for the comparison of etrasimod and placebo in the primary and key secondary endpoints. The family-wise type I error rate will be controlled at a fixed α level at 0.05 (2-sided) using the following testing procedure. First, the whole α will be spent on testing family 1 (F1) consisting of the coprimary endpoints. This study will be considered as an overall success only if both of the primary null hypotheses are rejected, each at the α level. This study will be considered as a partial success if only 1 of the 2 primary null hypotheses are rejected at $\alpha/2$ if the other has p-value $> \alpha$ (FDA 2017).

Figure 2 illustrates the parallel gatekeeping procedure, which will be followed to control the family-wise error rate.

Figure 2: Gatekeeping Procedure Summary

F1, family 1; F2, family 2, F3, family 3

Traditional Hochberg procedure:

Consider testing the family of hypotheses $H_{0i}; i = 1 \dots k$. Let p_i , for $i = 1 \dots k$, denote the sample p-values of tests for $H_{0i}; i = 1 \dots k$, computed without multiplicity adjustment. Let $[1] \dots [k]$ denote the random indices such that $p_{[1]} \leq \dots \leq p_{[k]}$ ($p_{[1]}$ is the smallest p-value, $p_{[k]}$ is the largest p-value). Hochberg procedure is implemented as follows:

Step 1: if $p_{[k]} < \alpha$, reject $H_{0[i]}, i = 1, \dots, k$ and stop; otherwise proceed to next step.

Step 2: if $p_{[k-1]} < \alpha/2$, reject $H_{0[i]}, i = 1, \dots, k-1$, and stop; otherwise proceed to next step.

...

Step k : if $p_{[1]} < \alpha/k$, reject $H_{0[1]}$, and stop; otherwise no null hypothesis is rejected.

Truncated Hochberg procedure (with truncation fraction f where $0 < f < 1$):

Consider testing the family of hypotheses $H_{0i}; i = 1 \dots k$. Let p_i , for $i = 1 \dots k$, denote the sample p-values of tests for $H_{0i}; i = 1 \dots k$, computed without multiplicity adjustment. Let $[1] \dots [k]$ denote the random indices such that $p_{[1]} \leq \dots \leq p_{[k]}$ ($p_{[1]}$ is the smallest p-value, $p_{[k]}$ is the largest p-value). Truncated Hochberg procedure is implemented as follows:

Step 1: if $p_{[k]} < f\alpha + (1-f)\alpha/k$, reject $H_{0[i]}, i = 1, \dots, k$ and stop; otherwise proceed to next step.

Step 2: if $p_{[k-1]} < f\alpha/2 + (1-f)\alpha/k$, reject $H_{0[i]}, i = 1, \dots, k-1$, and stop; otherwise proceed to next step.

...

Step k : if $p_{[1]} < f\alpha/k + (1-f)\alpha/k = \alpha/k$, reject $H_{0[1]}$, and stop; otherwise no null hypothesis is rejected.

A demonstration of alpha level for F3:

A truncation fraction $f = 0.8$ will be used in the truncated Hochberg procedure in testing F2, which results in the following alpha level to be passed to F3 for testing.

- All 4 null hypotheses in F2 are rejected:
 $\alpha(F3) = \alpha(F2) = 0.05$
- 3 of 4 null hypotheses in F2 are rejected:
 $\alpha(F3) = \alpha(F2) - [f\alpha(F2) + (1-f)\alpha(F2)/4] = 0.0075$
- 2 of 4 null hypotheses in F2 are rejected:
 $\alpha(F3) = \alpha(F2) - 2*[f\alpha(F2)/2 + (1-f)\alpha(F2)/4] = 0.005$
- 1 of 4 null hypotheses in F2 is rejected:
 $\alpha(F3) = \alpha(F2) - 3*[f\alpha(F2)/3 + (1-f)\alpha(F2)/4] = 0.0025$

8.5. Subgroup Analyses

The following subgroups will be assessed for the primary and key secondary endpoints:

- Sex (Female or Male)

- Age (\leq or $>$ Median, $<$ or ≥ 65)
- Race (White or Non-White)
- Region (North America, Western Europe, Eastern Europe, Other)
- Baseline oral corticosteroid usage (Yes or No)
- Naïve to biologic or JAK inhibitor therapy at study entry (Yes or No)
- Baseline disease activity (MMS: 4 to 6, 7 to 9)
- Actual Baseline MMS (5 to 7, 8 to 9)
- Baseline fecal calprotectin (\leq or $>$ Median)
- Baseline high-sensitivity C-reactive protein (\leq or $>$ Median)
- Baseline total Mayo score (TMS) (\leq or $>$ 8)
- Duration of UC (\leq or $>$ Median)
- Extent of disease (Proctosigmoiditis/Left-sided colitis, Pancolitis, Proctitis as reported on the eCRF)
- Proctitis (Yes or No, based on central read)
- Prior UC treatment of oral 5-aminosalicylic acid (5-ASA) only (Yes or No)
- Prior UC treatment failure of oral 5-ASA only (Yes or No)
- Number of prior biologic or JAK inhibitor therapies (1 or $>$ 1)
- Prior UC treatment failure of anti-tumor necrosis factor alpha (anti-TNF α) (Yes or No)

Additional subgroups may be assessed, if deemed necessary. The medians will be derived based on the FAS for all subgroups cut at the median. It should be noted that the study was not designed to detect treatment differences with high statistical power within subgroups. If any subgroup includes $<$ 5% of all subjects, no inferential statistics will be generated.

The actual stratum at Baseline will be used for all subgroup analyses.

Forest plots of the overall analysis set and all subgroups will be presented for each of the primary and key secondary endpoints. Inference from the model described in Section 16.1.3 will be used and differences in remission percentages along with 95% CIs will be displayed.

9. OUTPUT PRESENTATIONS

[Appendix 1](#) contains the conventions for presentation of data in outputs.

10. DISPOSITION AND PROTOCOL DEVIATIONS

All subjects who provide informed consent will be accounted for in this study. Inclusion criteria not met and exclusion criteria met will be listed.

Among the randomized subjects, the number and percent of subjects who completed/discontinued treatment, reasons off treatment, the number and percent of subjects who completed/discontinued the study, and reasons off study will be summarized. This summary will also be provided by region and country. The number and percent of subjects in each analysis set will be summarized for all randomized subjects. An additional summary of the number of subjects screened, the number of screen-failed subjects, and reason for screen failure will be presented for all screened subjects. A listing of subjects whose blind was broken will be provided. The number of subjects whose visit was impacted by the COVID-19 pandemic per CRF will also be summarized by nominal visit.

During site monitoring, protocol deviations will be graded as Critical, Major, or Minor.

According to ICH E3 and ICH E3(R1), important protocol deviations are a subset of protocol deviations that might significantly affect the completeness, accuracy, and/or reliability of the study data or that might significantly affect a subject's rights, safety, or well-being (ICH 1995, ICH 2012). For example, important protocol deviations might include enrolling subjects in violation of key eligibility criteria designed to ensure a specific subject population or failing to collect data necessary to interpret primary endpoints, as this may compromise the scientific value of the study.

During the review of all reported deviations, important deviations related to study inclusion or exclusion criteria, conduct of the study, patient management, or patient assessment will be identified. Where relevant the importance of a potentially important protocol deviations will be assessed in the context of the study's estimands to evaluate potential impact.

All important protocol deviations will be summarized for the FAS in the following categories in descending frequency in the etrasimod group.

All protocol deviations will be listed, including whether a deviation was impacted by the COVID-19 pandemic (Yes or No). Protocol deviation categories include but are not limited to the following:

- Informed Consent
- Eligibility and Entry Criteria
- Concomitant Medication
- Laboratory Assessment
- Study Procedures
- Serious Adverse Event
- Randomization
- Visit Schedule

- Investigational Product Compliance
- Efficacy
- Administrative
- Source Document
- Regulatory or Ethics Approvals
- Other

Important protocol deviations will also be summarized by whether they were impacted by COVID-19 pandemic (Yes or No). Additionally, a summary of missing endoscopy regardless of reason and missing endoscopy due to visit impacted by the COVID-19 pandemic will be presented by visit.

11. DEMOGRAPHIC AND BASELINE CHARACTERISTICS

The following demographic data and Baseline characteristics will be summarized for the FAS.

- Age on consent (years)
- Sex
- Race
- Ethnicity
- Woman of childbearing potential (Yes or No)
- Height (cm)
- Weight (kg)
- Body mass index (BMI) (kg/m²)
- Alcohol consumption (Yes or No)
- Caffeine consumption (Yes or No)
- Tobacco use (Yes or No)

This summary will be repeated for age, sex, race, ethnicity, or woman of childbearing potential for subjects who fail screening.

The following Baseline characteristics related to UC will be summarized:

- Extent of disease (Proctosigmoiditis/Left-sided colitis, Pancolitis, Proctitis reported on the electronic case report form [eCRF], and Proctitis reported from central reader review)
- Baseline MMS
- Baseline rectal bleeding (RB) subscore

-
- Baseline stool frequency (SF) subscore
 - Baseline endoscopic subscore
 - Baseline Physician's Global Assessment (PGA)
 - Baseline TMS
 - Duration of UC (years)
 - Any acute exacerbations within past 12 months (Yes or No), including the number of acute exacerbations among those with any acute exacerbation = Yes
 - Colonoscopy within past 12 months (Yes or No)
 - Surgery for UC (Yes or No), including the number of surgeries among those with surgery for UC = Yes
 - Hospitalizations for UC (Yes or No), including the number of hospitalizations
 - Naïve to biologic or JAK inhibitor therapy (Yes or No) – Reported (used for stratification at randomization)
 - Naïve to biologic or JAK inhibitor therapy (Yes or No) – Actual (medications reported on the eCRF)
 - Baseline corticosteroid use (Yes or No) – Reported (used for stratification at randomization)
 - Baseline corticosteroid use (Yes or No) – Actual (medications reported on the eCRF)
 - Baseline MMS group (4 to 6, 7 to 9) – Reported (used for stratification at randomization)
 - Baseline MMS group (4 to 6, 7 to 9, and 5 to 9) – Actual (scores reported on the eCRF)
 - Naïve to biologic or JAK inhibitor therapy – Difference between the Reported and the Actual
 - Baseline corticosteroid use (Yes or No) – Difference between the Reported and the Actual
 - Baseline MMS group (4 to 6, 7 to 9) – Difference between the Reported and the Actual
 - Prior failure of oral 5-ASA only (Yes or No)
 - Prior failure of anti-TNF α (Yes or No)
 - Prior failure of anti-TNF α or vedolizumab (Yes or No)

Prior treatment for UC will be summarized, including category of treatment, reason for discontinuation, and estimated duration (weeks) of corticosteroid use over the last 12 months.

11.1. Derivations

- Duration of UC (year) = (Informed consent date – Date of diagnosis + 1) / 365.25
- Weight (kg) = Weight (lb) × 0.4536
- Height (cm) = Height (in) × 2.54
- Height (m) = Height (in) × 0.0254 = Height (cm) × 0.01
- BMI (kg/m²) = Weight (kg) / Height (m)²

12. MEDICAL HISTORY

Medical history will be collected on the medical history eCRF and coded using Medical Dictionary for Regulatory Activities (MedDRA, v24.1). The version used to code medical history will be displayed in the outputs. All medical history will be summarized for the Safety Set by system organ class (SOC) and preferred term (PT).

13. MEDICATIONS

Medications will be captured on the Concomitant Medications eCRF and coded using the WHO Drug dictionary (WHODDE01SEP2021). Refer to [Appendix 2](#) for handling of partial dates for medications. In the case where it is not possible to define a medication as prior or concomitant, the medication will be classified by the worst case (ie, concomitant).

- ‘Prior’ medications are medications which started and stopped prior to the first dose of study treatment
- ‘Concomitant’ medications are medications which started prior to, on or after the first dose of study treatment AND ended on or after the date of first dose of study treatment or were ongoing at the end of the study

Concomitant medications will be summarized by Anatomical Therapeutic Chemical (ATC) Level 2 and Preferred Drug name for the Safety Set. Concomitant medications used for UC will be flagged as such on the Concomitant Medications eCRF and summarized by ATC Level 2 and Preferred Drug name for the Safety Set.

14. STUDY TREATMENT EXPOSURE

The date of first and last study treatment administration will be taken from the Day 1 Onsite Dosing Administration eCRF and the End of Study eCRF, respectively. Interruptions, compliance, and dose changes are not taken into account for duration of exposure. Exposure to study treatment in weeks will be summarized for the Safety Set.

Dose interruptions will be recorded on the Dosing Administration eCRF, and overdose will be recorded on the Overdose eCRF. The frequency and percentage of subjects who had at least

1 dose interruption, who had at least 1 dose interruption of > 7 days, who had at least 1 dose interruption of > 14 days, who had 1 overdose, and who had > 1 overdose will be summarized.

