6.3.1. Instructions for Missed Dose(s)

Subjects should be instructed that if they forget to take a dose, they can take the dose within 8 hours of the normal dosing time; otherwise, they should take their next dose at the regular time on the following day. If the subject vomits the tablet, he/she should be instructed not to take another tablet on the same day, but to take the next dose at the regular time on the following day. Missed doses should be recorded in the subject's electronic diary (eDiary), as indicated in the Schedule of Assessments, [Table 7](#) and [Table 8](#). Subjects should be instructed to contact the Investigator if they miss more than 2 consecutive doses.

Subjects who do not take the study treatment for ≥ 2 consecutive days within the first week of treatment or for ≥ 7 consecutive days after the first week of treatment must contact the Investigator to discuss treatment re-initiation. The subject must take the next dose of study treatment at the study site, and the in-clinic cardiac monitoring as outlined in Section 9.4.2.1 should be performed.

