6.3.2. Dose Interruptions

If the Investigator deems it necessary to withhold study treatment, temporary withholding is permitted for up to 6 days without obtaining prior approval from the Medical Monitor. If study treatment interruption ≥ 7 days is required for a medical reason, the Investigator must contact the Medical Monitor.

The first-dose monitoring as outlined in Section 9.4.2.1 should be performed any time a subject misses study treatment as follows:

- ≥ 2 consecutive days within the first week of treatment, or
- ≥ 7 consecutive days after the first week of treatment

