^d Due to overlapping windows in the RB/SF components at Week 52 and Week 48, a hierarchical algorithm will be used for the mapping. Week 52 will always be mapped first, then assess records for the Week 48 mapping. If a scheduled Week 48 and 52 visits are both present in the same visit window, they will be mapped to separate visits (ie, Week 48 and Week 52).

^e Assessments impacted by the COVID 19 pandemic are reported in the Date of Visit eCRF.

COVID-19, coronavirus disease 2019; ECG, electrocardiogram; eCRF, electronic case report form; MMS, modified Mayo Score; OCT, optical coherence tomography; PFT, pulmonary function test; RB, rectal bleeding; SF, stool frequency.

For cardiac remonitoring upon treatment reinitiation after Day 2, as manifested by more than 1 timed measurement in vital signs or electrocardiogram (ECG) parameters on the same collection date of an unscheduled visit, measurements will be mapped to analysis visit of Cardiac Remonitoring 1, Cardiac Remonitoring 2, etc. in the respective analysis dataset. For analysis, each timed measurement will be programmatically assigned to the nearest hourly timepoint (eg, Predose, 1-hour Postdose) based on their relationship to the dosing time on the same day. If the dosing date/time on the same day is missing, the timepoint will remain missing. Once mapped, these timed measurements from cardiac remonitoring visits will not be considered for any other analysis visit.

Windowing will be applied prior to any missing data calculations. The last nonmissing measurement taken prior to Day 1 (including unscheduled assessments) will be labeled as “Baseline”. Unless stated otherwise, data from all visits including scheduled, unscheduled, and ET visits will be eligible for allocation to an analysis visit. The 2-Week and 4-Week Follow-Up visits will not be included in the visit windows and will be summarized separately without any window applied.

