If one or more results for a variable are assigned to the same analysis visit, the result with the date closest to the protocol scheduled day will be used in the analysis, except for component subscores of MMS or TMS, in which case, the composite score and component subscores from the same date will be used in the analysis. If 2 measurements in the same analysis visit window are equidistant from the protocol scheduled study day, the earliest measurement will be used in the analysis. If multiple assessments are available on the same day, then the average of the assessment will be used in the analysis, except for laboratory and ECG data where the assessment at the earliest time of the same day will be used. If both central and local assessments of the same ECG or lab test are available on the same day, the central result will take precedence over the local result.

For the overlapping visit windows at Week 12 and Week 8/16, a hierarchical algorithm will be applied as follows: always map to the Week 12 study visit if the study day falls within the visit window of the Week 12 study visit, then assess the other records for the Week 8 or Week 16 study visit. The same algorithm will be used for Week 48 and Week 52, with Week 52 taking priority.

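### The SAP's dose-interruption rows do not line up with the protocol's monitored-restart triggers, and a restart recorded under a scheduled visit is not recognised as cardiac re-monitoring

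*SAP*

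**What the plan says.** **Triggers.** Protocol 6.3.2 sets the rule: "The first-dose monitoring as outlined in Section 9.4.2.1 should be performed any time a subject misses study treatment as follows", namely "≥ 2 consecutive days within the first week of treatment, or" "≥ 7 consecutive days after the first week of treatment". Protocol 6.3.1, 9.4.2.1 and Table 8 footnote e repeat the same two triggers. Protocol 6.3.2 also uses 7 days as the point from which the Medical Monitor must be contacted.

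**Place of restart.** Protocol 6.3.1: "The subject must take the next dose of study treatment at the study site". It does not require the visit to be unscheduled. Table 8 footnote e, which repeats the requirement, belongs to the scheduled-visit vital signs row.

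**Exposure table.** SAP 14 gives three nested rows for interruptions: any, "who had at least 1 dose interruption of > 7 days", and above 14 days.

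**Recognising re-monitoring.** SAP 6.4 maps measurements after Day 2 to Cardiac Remonitoring visits when a restart shows itself "as manifested by more than 1 timed measurement in vital signs or electrocardiogram (ECG) parameters on the same collection date of an unscheduled visit". Data mapped in this way are barred from every other analysis visit.

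**Same-day rule.** SAP 6.4: "If multiple assessments are available on the same day, then the average of the assessment will be used in the analysis". Laboratory and ECG data are excepted and take the earliest value of the day.

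**The concern.** Bradycardia at the first dose and AV block are named class risks in Protocol 1.3, and SAP 18.1.5 lists bradycardia and AV conduction delay among the events of special interest. A reader of the study report will want to know how many subjects met the restart-monitoring trigger and what their heart rates did. The exposure table cannot answer the first question, because its cut points are not the protocol's.

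The second question is answered only for restarts that carry the re-monitoring label. That label depends on the visit type rather than on the interruption that made the monitoring necessary. A restart on a scheduled visit day is foreseeable, since doses on visit days are already taken at the site. The SAP intends restart readings to be kept out of ordinary visit values, and for such a restart its own rule defeats that intention.

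**Working it through.** The plan states no figure on this point, so there is none to reproduce. The check compares cut points, traces the mapping rules, and works one example.

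**1. Interruption lengths against triggers and rows**

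Inputs: the triggers in Protocol 6.3.2 and the rows in SAP 14. Whole-day lengths from 1 to 21 days were enumerated.

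| Trigger met | Lengths that trigger | Of these, not in the > 7-day row |
|---|---|---|
| First week | 2 days or more | 2, 3, 4, 5, 6, 7 |
| After the first week | 7 days or more | 7 |

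All of these lengths are in the any-interruption row, so none is lost from the count. Conversely, every interruption above 7 days meets a trigger. The number of subjects meeting a trigger therefore lies somewhere between the > 7-day count and the any-interruption count, and the table cannot say where.

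**2. Mapping of a restart after Day 2 under SAP 6.4**

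| | Recorded under an unscheduled visit | Recorded under a scheduled visit |
|---|---|---|
| Mapped to Cardiac Remonitoring | Yes, by hour | No |
| Kept out of ordinary visit values | Yes | No |
| Vital signs | Hourly values retained | Pre-dose and post-dose averaged into the visit value |
| ECG | Hourly values retained | Not averaged; earliest value of the day |
| Dedicated re-monitoring listing (SAP 18.5) | Included | Not labelled for it |
| 4-hour criterion (SAP Table 4) | Applies | Not labelled for it |
| Individual readings in abnormality and worst-case summaries (SAP 6.3) | Yes | Yes |

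**3. Size of the shift in one visit value**

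The documents give no restart heart rates, so the readings below are assumptions. They are ordered pre-dose, then Hours 1, 2, 3 and 4. The visit value is the sum of the five readings divided by 5.

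| Assumed readings (bpm) | Visit value | Pre-dose | Shift |
|---|---|---|---|
| 72, 66, 60, 58, 62 | 318/5 = 63.6 | 72 | −8.4 |
| 65, 58, 50, 46, 49 | 268/5 = 53.6 | 65 | −11.4 |
| 66, 58, 51, 47, 49 | 271/5 = 54.2 | 66 | −11.8 |
| 72, 62, 54, 48, 56 | 292/5 = 58.4 | 72 | −13.6 |

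Take the third row as a restart at the Week 8 visit. The Hour 4 reading of 49 is below 50 bpm, and the fall from pre-dose is 66 − 49 = 17 bpm, which exceeds 10. Both numerical parts of the Table 4 4-hour criterion are met. That criterion is confined to Day 1, Day 2 and re-monitoring visits, so without the label it is not applied. The readings of 47 and 49 still count as below 50 bpm under SAP 6.3.

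**The case against.** The strongest reply is that little is lost. SAP 14 counts every interruption in its first row and is a descriptive exposure table that does not claim to count monitored restarts. Restarts at unscheduled visits are handled properly: they are mapped by hour, excluded from other visits and listed. SAP 18.5 lists all vital signs. The scheduled-visit problem arises only if the eCRF stores the timed readings under the scheduled visit. It may instead store them as an unscheduled visit on the same date, and the documents do not show which. Table 8 footnote e also describes the visit vital signs as taken before dosing.

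Most of this is right and limits the point, but it does not remove it. The row boundaries still differ from the protocol's, and SAP 6.4 still relies on visit type without saying how a restart on a scheduled visit day is to be recorded.

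Three stronger readings are tempting and are not supported:

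- **Triggering interruptions are missed.** They are counted; they are only not separable.
- **Restart bradycardia is averaged out of the abnormality counts.** SAP 6.3 brings all measurements into the summaries of abnormalities and worst-case values.
- **The distortion falls mainly on the etrasimod arm.** Monitored restarts apply to both blinded arms, and the documents give no restart counts by arm.

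**Conclusion.** The point holds as a minor defect in exposure and safety reporting. The mismatch in SAP 14 follows directly from the text. The effect in SAP 6.4 is conditional on a restart being recorded under a scheduled visit. In that case the visit's vital signs mix pre-dose and post-dose readings, and the subject loses the label for the re-monitoring listing and the 4-hour criterion. The shift in a single subject's visit heart rate is −8.4 to −13.6 bpm in the worked examples, which rest on assumed readings. The effect on group means cannot be sized, because the number of such restarts is unknown and may be nil. The ECG values are not averaged, and the primary and key secondary efficacy analyses are not affected.

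**What to change.** - **SAP 14:** report rows at the protocol's existing triggers (2 or more consecutive days in the first week; 7 or more consecutive days thereafter) and keep the row above 14 days.
- **SAP 6.4, identification:** define Cardiac Remonitoring as timed post-dose measurements on the restart date after a qualifying interruption on the Dosing Administration eCRF, whether the visit is scheduled or unscheduled. Linking it to the interruption is better than accepting any date with more than one timed reading, which would relabel a simple repeat reading at an ordinary visit.
- **SAP 6.4, scheduled-visit restart:** use the pre-dose reading as the visit value and also as the Predose timepoint for re-monitoring. Map the post-dose readings to Cardiac Remonitoring, so that the SAP 18.5 listing and the Table 4 4-hour criterion apply.

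No clinical rule changes, because the triggers are those already in the protocol. SAP 14 already records interruptions on the Dosing Administration eCRF. The fix assumes that runs of missed doses meeting a trigger are entered there and not only in the eDiary, which should be confirmed. The cost is a few lines of SAP text and minor programming.
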